APPENDIX SECTION:

APPENDIX A INFORMED CONSENT

APPENDIX B ELIGIBILITY CHECKLIST

APPENDIX C COMMON TOXICITY CRITERIA

APPENDIX D ECOG PERFORMANCE STATUS

APPENDIX E CASE REPORT FORMS

1.0 OBJECTIVE

1.1 Primary Objective

1.1.1. To evaluate the maximum tolerated dose of nanoliposomal irinotecan with continuous low-dose temozolomide for patients with recurrent glioblastoma.

1.1.2 To assess the preliminary response rate and progression free survival of nanoliposomal irinotecan with continuous low-dose temozolomide in patients with recurrent glioblastoma.

1.2 Secondary Objectives

1.2.1 To evaluate the safety of nanoliposomal irinotecan with continuous low-dose temozolomide.

2.0 BACKGROUND

Glioblastoma: There are approximately 14,000 new cases of malignant brain tumors diagnosed each year in the United States.¹ Glioblastomas account for approximately 60 to 70% of malignant gliomas.¹ They are the most aggressive form of primary brain tumors and are characterized by areas of microvascular proliferation, necrosis, or both.² Patients with high-grade glioma typically present with subacute and progressive neurologic signs and symptoms that vary according to the location of the tumor within the brain. Headache is the most common presenting symptom, which is present in over half of patients at time of diagnosis.³

Temozolomide and Radiation is the Standard First-Line Treatment for GBM: High-grade gliomas are rapidly progressive tumors that are best managed with a combined modality approach, incorporating maximal surgical resection, adjuvant postoperative radiation therapy, and adjuvant chemotherapy.³ In a phase III study by the European Organization for Research and Treatment of Cancer (EORTC) and the National Cancer Institute of Canada (NCIC) compared standard radiation alone to radiation and temozolomide. Temozolomide was administered daily throughout radiation then continued as a maintenance for 5 consecutive days of a 28-day cycle. There was an increase in median survival (14.6 months vs 12.1 months, $p < 0.0001$) with the addition of temozolomide to radiation as compared to radiation alone.⁴ Furthermore, there was an improvement in 2-year survival with temozolomide and radiation as compared to radiation alone, 26.5% vs 10.4%, respectively.⁴

Metronomic Temozolomide For Recurrent GBM: Relapse after first line therapy is inevitable. Rechallenge with dose-dense TMZ schedules such as continuous dose (metronomic) schedules for recurrent GBM is recommended for patients who relapse on standard maintenance temozolomide.^{5,6} Continuous therapy with metronomic regimens may inhibit tumor angiogenesis through the suppression of tumor endothelium regeneration and MGMT depletion of the tumor endothelium.⁷⁻⁹

Multiple studies have demonstrated modest benefit with continuous low-dose TMZ and this has become a standard treatment in recurrent GBM.^{10,11} In a phase II study by Wick et al, 90 patients with recurrent GBM received temozolomide weekly, 1 week on and 1 week off. The median survival time from diagnosis of progression was 38 weeks (95% CI, 30 to 46 weeks), and the 1-year survival rate from progression was 23%.¹¹ O6-methylguanine DNA methyltransferase (MGMT) gene promoter methylation in the tumor tissue

was not associated with longer PFS (log-rank $P = .37$) implying that continuous TMZ is also active in patients with tumors lacking MGMT gene promoter methylation.

Woo et al administered TMZ daily at 50 mg/m²/day in 30 patients with recurrent GBM. The median progression-free survival was 2 months (range, 0.5–16). At 6 months, PFS was 20%. The median overall survival from the start of therapy to death was 6 months (95% CI : 5.1–6.9).¹² The response rate is approximately 5-10%. This continuous low dose daily regimen (metronomic schedule) is probably the most commonly utilized regimen across the country and the standard practice within the Brown University Oncology Research Group affiliated hospitals.

More Effective Agents in Combination with Metronomic TMZ are needed. While metronomic TMZ is commonly used in GBM, the benefits are very modest and more effective agents are needed. Unfortunately, the addition of bevacizumab to continuous low-dose TMZ was not superior to temozolomide alone in terms of progression-free or overall survival.¹³

Irinotecan In GBM: Irinotecan has modest activity in GBM. In a study by Friedman et al, 9 of 60 patients (16%) with progressive or recurrent GBM had a partial response to irinotecan.¹⁴ A randomized study of 167 patients evaluated the efficacy of bevacizumab, alone and in combination with irinotecan in patients with recurrent glioblastoma.¹⁵ In the bevacizumab-alone and the bevacizumab-plus-irinotecan groups, estimated 6-month progression-free survival rates were 42.6% and 50.3%, respectively; objective response rates were 28.2% and 37.8%, respectively; and median overall survival times were 9.2 months and 8.7 months.

The nanoliposomal irinotecan More Effectively Crosses the Blood Barrier: Irinotecan has modest activity in glioblastoma. The blood brain barrier markedly reduces drug absorption preventing irinotecan the opportunity to reach its target in the brain.¹⁶ Nanoliposomal irinotecan is a nanoliposomal encapsulation of irinotecan. A nanoliposome, or submicron bilayer lipid vesicle, is a new technology for the encapsulation and delivery of bioactive agents. Nanoliposomes improve the solubility and bioavailable of irinotecan markedly increasing the ability of irinotecan to cross the blood brain barrier. For example Noble et al, evaluated a nanoliposomal irinotecan as an intravenous treatment in an intracranial U87MG brain tumor model in mice, and irinotecan and SN-38 levels were analyzed in malignant and normal tissues.¹⁷ Tissue analysis demonstrated favorable properties for nanoliposomal irinotecan, including a 10.9-fold increase in tumor AUC for drug compared with free irinotecan and 35-fold selectivity for tumor versus normal tissue exposure.¹⁷

Onivyde is FDA Approved in Advanced Pancreatic Cancer: The NAPOLI-1 trial randomized 417 patients with metastatic pancreatic adenocarcinoma that progressed after treatment with gemcitabine-based chemotherapy. Patients received either the nanoliposomal irinotecan (Onivyde) as a single agent, in combination with 5-Fluorouracil and leucovorin (5-FU/LV), or 5-FU/LV alone (control arm). The median survival in the combination therapy arm with Onivyde/5-FU/LV was

(6.1 vs 4.2 months; unstratified hazard ratio [HR], 0.67 [95% confidence interval (CI), 0.49-0.92]; $P = 0.012$).¹⁸ There was also an improvement in PFS to a median of 3.1 months with the irinotecan liposomal plus 5-FU/LV group as compared with 1.5 months for those receiving 5-FU/LV alone.¹⁸ These results led to FDA approval for Onivyde.

Rationale for Combining nanoliposomal irinotecan and Temozolomide: Multiple in-vitro and clinical trials support the rationale for combining a topoisomerase I inhibitor such as irinotecan and an alkylating agent such as temozolomide.¹⁹⁻²¹ The principle mechanism of action of a topoisomerase I inhibitor is mainly S phase specific inhibiting DNA replication. In contrast an alkylating agent directly damages DNA. The combination of a topoisomerase inhibitor with an alkylating agent is a rational, established strategy for increasing tumor-cell kill.¹⁹⁻²¹

Protocol Rationale: New treatments are greatly needed for patients with recurrent glioblastoma. Metronomic temozolomide is a standard treatment option but has, at best, modest activity. The nanoliposomal irinotecan may be much more active than the parent compound irinotecan since nanoliposomal irinotecan's ability to cross the blood brain barrier is improved. The combination of a topoisomerase inhibitor and an alkylating agent has strong preclinical and clinical rationale. This phase I study will establish the MTD of the combination of nanoliposomal irinotecan in combination with temozolomide and preliminary clinical efficacy of the combination of nanoliposomal irinotecan and metronomic temozolomide.

3.0 PATIENT ELIGIBILITY

3.1 Conditions for Patient Eligibility

3.1.1 Histologically confirmed glioblastoma multiforme (gliosarcoma also eligible), Pathology report to be sent to BrUOG.

3.1.2 Progression or recurrence after at least one line of therapy. Patient must have received temozolomide and radiation but it is not required that they were given concurrently. This does not include clinical progression.

3.1.3 Age ≥ 18 years

3.1.4 Karnofsky performance score ≥ 60

3.1.5 Life expectancy >12 weeks as noted by treating investigator

3.1.6 Laboratory results requirements

- Absolute neutrophil count (ANC) $\geq 1500/\text{mm}^3$.
- Platelets (Plt) $\geq 100,000/\text{mm}^3$
- Hemoglobin (Hgb) $\geq 9.0 \text{ g/dL}$
- Total bilirubin $\leq 1x \text{ ULN}$
- Albumin levels $\geq 3.0 \text{ g/dL}$
- Aspartate aminotransferase (AST) and alanine aminotransferase (ALT) $\leq 2.5 \times \text{ ULN}$
- Serum creatinine $\leq 1.5 \times \text{ ULN}$

3.1.7 . Not pregnant and not nursing. Women of child bearing potential must have a negative serum pregnancy test (minimum sensitivity 25 IU/L or equivalent units of HCG) within 7 days prior to Day 1 of treatment. Post-menopausal women (surgical menopause or lack of menses ≥ 12 months) do not need to have a pregnancy test, please document status.

3.1.8. Confirmation of informed consent.

3.1.9 . Men and women of childbearing potential enrolled in this study must agree to use adequate barrier birth control measures during the course of the study and for at least 2 months after the last treatment on study.

3.1.10 Recovered (\leq grade 1) from clinically significant effects of any prior surgery, radiotherapy or other anti-neoplastic therapy, except alopecia or hematological laboratory values (see 3.1.6 for required values for the trial).

3.1.11 Stable corticosteroid dose at least 7 days prior to day 1

3.1.12 Patient must have assessable (measurable) disease at baseline by brain MRI. Must be contrast enhancing. The tumor size will be measured in millimeters and is the largest cross-sectional area using perpendicular measurements of contrast enhancing abnormality.

3.2.13 Patient must be able to tolerate brain MRI with contrast

3.2 Exclusion Criteria

3.2.1 Non-GBM primary invasive malignant neoplasm that is considered by treating investigator to likely cause death in the next 5 years.

3.2.3 Radiation therapy or cytotoxic chemotherapy or biologics or immunotherapy within previous three weeks from day 1 of drug (no anticancer treatment of any kind within 3 weeks of day 1 of drug- steroids are acceptable if stable dose per 3.1.11).

3.2.4 Patient not to be receiving any cancer therapy or investigational anti-cancer drug.

3.2.5 Evidence of an active infection requiring intravenous antibiotic therapy

3.2.6 Any medical condition that in the opinion of the Investigator may interfere with a subject's participation in or compliance with the study. Must receive confirmation in writing from treating MD.

3.2.7 Pregnant or breast feeding; females of child-bearing potential must test negative for pregnancy at the time of enrollment based on serum pregnancy test.

3.2.8 Unwillingness or inability to follow the procedures required in the protocol, site to have documentation to confirm at time of registration that this is not the case.

3.2.9 Patient with a history of Gilbert's disease or known UGT1A1*28 allele. (Assessment for the UGT1A1*28 allele is not required for protocol entry.) Documentation required at time of study entry by treating MD.

3.2.10 myocardial infarction, unstable angina pectoris, stroke within 6 months of study registration.

3.2.11 NYHA Class III or IV congestive heart failure

3.2.12 Known hypersensitivity to any of the components of nanoliposomal irinotecan , other liposomal products, or temozolomide. Must be documented by treating MD.

3.2.13 Investigational anticancer therapy administered within 4 weeks of day 1 (the first scheduled day of dosing in this study). Site must submit all prior investigational agents with last dose administered and half-life for BrUOG review.

3.2.14 Live vaccines within 30 days prior to the first dose of trial treatment and while participating in the trial. Examples of live vaccines include, but are not limited to, the following: measles, mumps, rubella, chicken pox, yellow fever, rabies, BCG, and typhoid (oral) vaccine. Seasonal influenza vaccines for injection are generally killed virus vaccines and are allowed; however, intranasal influenza vaccines (e.g., Flu-Mist®) are live attenuated vaccines and are not allowed. All recent vaccines (within 30 days) to be listed on conmed log and submitted to BrUOG.

3.2.15 Use of strong CYP3A4 inducers is not allowed and patients must be off any of these exclusionary products for \geq 2 weeks from day 1. The use of strong CYP3A4 inducers (rifampin, phenytoin, carbamazepine, rifabutin, rifapentine, phenobarbital, St. John's wort, nevirapine, fosphenytoin, pentobarbital, primidone, enzalutamide, lumacaftor, mitotane, apalutamide, quinine) should not be used during the trial. If possible, substitute non-enzyme inducing therapies at least 2 weeks prior to treatment day 1.

3.3 Re-Screening:

Re-screening is defined in this protocol as screening a patient for this trial, once they have been found to not meet study eligibility criteria, outside of the 28-day screening window. While in the 28 day screening window, the patient may be screened multiple times (i.e. labs may be drawn and re-drawn), however, if a patient signs consent and then screen fails (does not meet the eligibility criteria) and the treating MD requests that the patient be re-screened outside of the 28 day screening window, sites are to contact BrUOG who will assess patients on a case by case basis. Depending on many diverse factors including the conditions that are being evaluated, the reasons why patient initially screen failed, and the nature of the initial results, re-screening may or may not be medically/scientifically appropriate. BrUOG should be made aware of such a situation with at least 72 hours and provided with information on screen-failure.

4.0 TREATMENT

Cycle = 2 weeks (14 days)

Temozolomide: 50mg/m²/day until disease progression. Even though temozolomide will be given continuously, data will be captured by cycle with study drug. See section 5.3 for dose reduction information. Patients to receive enough TMZ pills for 2 cycles at a time (with refills on the prescription) and to align with the standard manner in which TMZ is prescribed. However, in order for research staff to confirm drug compliance and that a new cycle can begin, patients are encouraged to bring in TMZ and drug diary at the beginning of each new cycle. If a patient requires a reduced dose of TMZ in the middle of their prescription (prior to a new 28 day supply being written), the treating physician and research staff will communicate the dose reduction and manner in which the patient must take their pills for the remaining days of the drug supply.

	Dose Level -1	Dose Level 1
Temozolomide	25mg/m ² /day	50mg/m ² /day

Nanoliposomal irinotecan :

Dose Level 1 50mg/m² IV every 2 weeks

Dose Level 2 70 mg/m² IV every 2 weeks

Dose Level 3 80mg/m² IV every 2 weeks

	Dose Level -1	Dose Level 1	Dose Level 2	Dose Level 3
Nanoliposomal irinotecan	43 mg/m ² , day 1	50 mg/m ² , day 1	70 mg/m ² , day 1	80 mg/m ² , day 1

Doses do not need to be re-calculated unless there is a 10% change in weight or at the discretion of the treating physician if done more frequently.

(If nanoliposomal irinotecan dose level 1 exceeds the definition of maximum tolerated dose, as described below, then dose level -1 of nanoliposomal irinotecan, 43mg/m² IV every 2 weeks with temozolomide 50mg/m²/day will be investigated.)

7/21/16, 7/26/16, 8/1/16, 8/2/16, 8/3/16, 8/4/16, 8/9/16, 8/15/16, 8/16/16, 8/17/16 submitted Merrimack, 10/3/16 Merrimack edits, 10/7/16. 7
Re-submitted Merrimack 10/11/16, 11/15/16 from Merrimack, 11/17/16, 11/30/16 back to Merrimack, approved Merrimack 1/5/17,
1/26/17, 2/7/17 company review, 2/8/17, 2/13/17, 3/2/17 company, 3/3/17, approved company 3/23/17, RN/Pharmacy/EXEC review
3/31/17, 3/31/17 BrUOG, to company 4/6/17, Ipsen 4/18/17, BrUOG 4/20/17, Ipsen approved 5-4-17, FDA 5-5-17, FDA IND exemption
5/18/17, Protocol change 5/18/17, Protocol change 7/10/17 with IB v10, 8/17/17, Amendment # 1 4/6/18, Amendment #2 8/14/18,
Amendment # 3 12/8/18

Nanoliposomal irinotecan will be administered by IV infusion over approximately 90 minutes. One cycle is 14 days, subsequent doses should be administered on the first day of each cycle +/- 3 days. An additional 1 day is provided for a holiday.

Three patients will be accrued to level 1. If no dose limiting toxicities are observed following completion of 4 weeks (2 cycles) of treatment then accrual to dose level 2 will proceed (patients must be evaluated prior to their cycle 3 treatment and this will be used to confirm DLTs). If a DLT is observed in one of the first 3 patients in a dose level, then accrual for that level will be expanded to 6 patients. Accrual will continue in this way until the MTD of nanoliposomal irinotecan with temozolomide 50mg/m²/day is determined. Two or more instances of DLT in a cohort of 6 patients will result in the preceding dose level being defined as the MTD. If two or more instances of DLT in a cohort of 6 patients occurs in dose level 1 then dose level -1 of nanoliposomal irinotecan will be investigated. After determination of the MTD, the final cohort will be expanded so that a total of 25 patients are treated on study. The final cohort will be treated at the MTD.

If a patient is unable to receive 4 weeks of treatment (2 cycles) for reasons other than dose limiting toxicity, they will be replaced in a cohort.

Premedication

All patients must be premedicated prior to nanoliposomal irinotecan infusion with standard doses of dexamethasone and a 5-HT3 antagonist or other anti-emetics as per standard institutional practices for irinotecan administration. Atropine may be prescribed prophylactically for patients who experienced acute cholinergic symptoms in previous cycles.

Premedication prior to temozolomide is not required and may be administered as per institutional standard of care.

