5.1 Treatment Delay

A new course of treatment (cycle) with nanoliposomal irinotecan and temozolomide should not begin until the following criteria are met.

- Platelets $\geq 100,000 \times 10^9/L$ (100,000/mm³)
- Granulocytes (ANC) $\geq 1.5 \times 10^9/L$ (1,500/mm³)
- Recovery from other clinically significant, treatment related non-hematologic toxicities to \leq Grade 2

*please refer to section 5.2 for events that require dose reductions cycles 3-on*The treating physician may decide to hold treatment secondary to other toxicities even if deemed not related to treatment if the physician feels it is in the patient's best interest. This must be documented and submitted to BrUOG on treatment form and AE log.

If the patient does not meet these criteria at the start of a scheduled cycle, treatment should be delayed until these requirements are met.

Patients who require a treatment delay of more than 4 weeks due to toxicity will be removed from protocol treatment. Patients who require a treatment delay of more than 8 weeks not due to toxicity will be removed from protocol treatment.

If a patient is unable to receive 4 weeks of treatment (2 cycles) for reasons other than a dose limiting toxicity, they will be replaced in a cohort.

5.2 Definition of Dose Limiting Toxicities:

Dose limiting toxicities will be defined as the following toxicities occurring during the first 2 cycles (28 days) of therapies. If however a patient experiences one of the below toxicities after cycle 2 they will be dose reduced (both drugs), even though it will no longer be defined as a DLT.

- Grade 4 neutropenia (ANC < 500/mm³) for > 7 days
- ANC < 1000/mm³ with fever or infection
- Platelets < 25,000/mm³
- Platelets < 50,000/mm³ requiring transfusion
- Grade 3 or 4 treatment related non-hematologic toxicities excluding alopecia.
 - Grade 3 nausea, vomiting or diarrhea will only be considered a dose limiting toxicity if it occurs for greater than 72 hours despite maximal medical support.
 - Grade 3 electrolyte abnormalities will not be considered dose limiting toxicities if the electrolyte disorder can be corrected to grade 2 or less within 72 hours.
 - A grade 4 electrolyte abnormality will be considered a DLT.
- Delay of treatment for > 2 weeks due to toxicity (do not score a second DLT for a treatment delay caused by the same event)

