10.1 Treatment Compliance

Records of nanoliposomal irinotecan used, dosages administered, and intervals between visits will be recorded during the study. Drug accountability will be noted.

All drugs will be administered to eligible patients under the supervision of the investigator or identified sub-investigator(s). The pharmacist will maintain records of drug receipt drug preparation, and dispensing, including the applicable lot numbers. Any discrepancy between the calculated dose and dose administered and the reason for the discrepancy must be recorded in the source documents.

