17.0 STATISTICS

SAMPLE SIZE AND STATISTICAL DESIGN

Three patients will be accrued to level 1. If no dose limiting toxicities are observed following completion

7/21/16, 7/26/16, 8/1/16, 8/2/16, 8/3/16, 8/4/16, 8/9/16, 8/15/16, 8/16/16, 8/17/16 submitted Merrimack, 10/3/16 Merrimack edits, 10/7/16. 32
Re-submitted Merrimack 10/11/16, 11/15/16 from Merrimack, 11/17/16, 11/30/16 back to Merrimack, approved Merrimack 1/5/17,
1/26/17, 2/7/17 company review, 2/8/17, 2/13/17, 3/2/17 company, 3/3/17, approved company 3/23/17, RN/Pharmacy/EXEC review
3/31/17, 3/31/17 BrUOG, to company 4/6/17, Ipsen 4/18/17, BrUOG 4/20/17, Ipsen approved 5-4-17, FDA 5-5-17, FDA IND exemption
5/18/17, Protocol change 5/18/17, Protocol change 7/10/17 with IB v10, 8/17/17, Amendment # 1 4/6/18, Amendment #2 8/14/18,
Amendment # 3 12/8/18

of 4 weeks of treatment (2 cycles) then accrual to dose level 2 will proceed. If a DLT is observed in one of the first 3 patients in a dose level, then accrual for that level will be expanded to 6 patients. Accrual will continue in this way until the MTD is determined. Two or more instances of DLT in a cohort of 6 patients will result in the preceding dose level being defined as the MTD. After determination of the MTD, the final cohort will be expanded so that a total of 25 patients are treated on study. The final cohort will be treated at the MTD.

If a patient is unable to receive 4 weeks of treatment (2 cycles) for reasons other than a dose limiting toxicity, they will be replaced in a cohort. Patients who require a treatment delay of more than 8 weeks not due to toxicity will be removed from protocol treatment.

If two or more instances of DLT in a cohort of 6 patients occurs in dose level 1 then dose level -1 of nanoliposomal irinotecan will be investigated.

Definition of Dose Limiting Toxicities

- Grade 4 neutropenia (ANC < 500/mm³)
- ANC <1000/mm³ with fever (temp > 101) or infection
- Grade 4 thrombocytopenia: Platelets <25,000/mm³
- Platelets <50,000/mm³ requiring transfusion
- Grade 3 or 4 treatment related non-hematologic toxicities excluding alopecia.
 - Grade 3 nausea, vomiting or diarrhea will only be considered a dose limiting toxicity if it occurs for greater than 72 hours despite maximal medical support.
 - Grade 3 electrolyte abnormalities will not be considered dose limiting toxicities if the electrolyte disorder can be corrected to grade 2 or less within 72 hours.
 - A grade 4 electrolyte abnormality will be considered a DLT.

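### Return of temozolomide capsules and diary is optional and DLT evaluability has no minimum temozolomide exposure, so unrecognised under-dosing in cycles 1-2 could push the combination MTD upward

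*Combined protocol and SAP*

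**What the plan says.** All references are to the combined protocol and SAP.

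- **Target.** Section 4.0 continues accrual "until the MTD of nanoliposomal irinotecan with temozolomide 50mg/m²/day is determined". The MTD is thus a statement about two drugs, one of them at a fixed dose.
- **Window.** Section 5.2 counts DLTs "occurring during the first 2 cycles (28 days) of therapies".
- **Supply.** Section 4.0: "Patients to receive enough TMZ pills for 2 cycles at a time". One dispensing covers the whole window.
- **Verification.** Section 4.0 gives the aim, "in order for research staff to confirm drug compliance and that a new cycle can begin", and then the means: "patients are encouraged to bring in TMZ and drug diary at the beginning of each new cycle". It adds: "Even though temozolomide will be given continuously, data will be captured by cycle with study drug". By contrast, the clinical evaluation before cycle 3 is mandatory. The study calendar in section 6.0 has no row for a diary review or capsule count.
- **Records.** Section 10.0 requires inventory records for nanoliposomal irinotecan. Section 10.1 opens: "Records of nanoliposomal irinotecan used, dosages administered, and intervals between visits will be recorded during the study". The same section also has a rule on recording discrepancies between calculated and administered dose, and that rule is not limited to one drug.
- **Who counts.** Section 17.0, in line with 4.0 and 5.1, replaces a patient in the cohort under this condition: "If a patient is unable to receive 4 weeks of treatment (2 cycles) for reasons other than a dose limiting toxicity". No amount of temozolomide is attached to it. Section 5.3 defines a temozolomide cycle as daily dosing for 14 days.

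**The concern.** A patient who is free of DLT after 28 days is evidence about the combination only if the combination was taken. The infusions are given in clinic and are certain. Temozolomide intake depends on what the patient does at home, and the one direct check named in the plan may be skipped.

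Two gaps follow. First, under-dosing may go undetected if capsules and diary are not brought back. Second, even when it is known, nothing says how many missed doses make a patient non-evaluable. The word 'unable' fits poorly with a patient who simply did not take the capsules.

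Both drugs can contribute to the hematologic DLTs. Section 9.2 lists thrombocytopenia and leukopenia for temozolomide and mentions first-cycle Grade 4 neutropenia. Section 9.1.5 warns of severe neutropenia with irinotecan. In cohorts of 3 to 6, one wrongly counted patient can decide whether a level is cleared. The level chosen is then used for the expansion to 25 treated patients. Intake data that were not collected at the time cannot be recovered at analysis.

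**Working it through.** The plan states no adherence rate, no target DLT rate and no operating characteristics for its escalation rule, so it has no figure of its own to reproduce here. The calculation is an illustration under stated assumptions.

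**From the documents.** A level is cleared with 0 DLTs in 3 patients, or with 1 in the first 3 and none in the next 3. Two or more in 6 fails the level (sections 4.0 and 17.0).

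**Assumed.** A share f of counted patients is under-exposed to temozolomide without this being recognised. The DLT probability is p_full with full dosing and p_low with little temozolomide.

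**Formulas.**

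- DLT rate among counted patients: q = (1 − f) × p_full + f × p_low
- Chance of clearing the level: P = (1 − q)³ + 3q(1 − q)² × (1 − q)³ = (1 − q)³ + 3q(1 − q)⁵

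**Main case, p_full = 0.35 and p_low = 0.15.**

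| f | q | (1 − q)³ | 3q(1 − q)⁵ | P |
|---|---|---|---|---|
| 0 | 0.350 | 0.2746 | 0.1218 | 0.396 |
| 5% | 0.340 | 0.2875 | 0.1277 | 0.415 |
| 10% | 0.330 | 0.3008 | 0.1337 | 0.434 |
| 20% | 0.310 | 0.3285 | 0.1455 | 0.474 |
| one third | 0.283 | 0.3681 | 0.1607 | 0.529 |

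**Other assumed rates, same formulas.**

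| p_full | p_low | f = 0 | f = 10% | f = 20% | f = 30% |
|---|---|---|---|---|---|
| 0.30 | 0.20 | 0.494 | 0.515 | 0.536 | 0.557 |
| 0.30 | 0.10 | 0.494 | 0.536 | 0.578 | 0.622 |
| 0.40 | 0.20 | 0.309 | 0.343 | 0.378 | 0.415 |
| 0.40 | 0.10 | 0.309 | 0.360 | 0.415 | 0.474 |
| 0.50 | 0.20 | 0.172 | 0.208 | 0.248 | 0.293 |
| 0.50 | 0.10 | 0.172 | 0.221 | 0.278 | 0.343 |

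P falls as q rises, so unrecognised under-exposure raises P whenever p_low is below p_full. The shift is zero if f = 0, if under-exposed patients are recognised and replaced, or if temozolomide adds nothing to the DLT risk.

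**The case against.** The strongest reply is that the plan already intends what is asked for. Section 4.0 says staff are to confirm compliance and that temozolomide data are captured by cycle. The discrepancy rule in section 10.1 is general, and section 12.0 lists major noncompliance as a reason for removal. Section 5.3 makes a temozolomide cycle 14 daily doses, so two infusions alone are not two cycles, and a patient known to be under-exposed can be read as replaceable. The case report forms are attached separately and may record doses taken.

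Much of this stands, and it rules out three stronger readings that a reader might infer.

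- *Temozolomide intake is not recorded.* The documents do not show that. They state an intention to capture it. Section 10.0 is an inventory rule for the supplied drug, so its silence on a commercially prescribed drug says little.
- *Two infusions are enough to be counted.* The text does not say so. It leaves the matter open, because the rule names no threshold and speaks of inability.
- *The MTD is biased upward.* No adherence or DLT rate in the documents supports this as fact. Undetected over-intake would act in the other direction. At 5% to 10% under-exposed, the main case moves only from 0.396 to 0.415-0.434.

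What the reply does not remove is the gap itself. Capture by cycle and the discrepancy rule both need a source for doses taken at home, and the only source named is optional. Removal for noncompliance sets no temozolomide threshold and does not say whether the removed patient counts for the MTD. Complete records would still leave open who is DLT-evaluable.

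**Conclusion.** The point holds as a conditional risk. The plan intends to confirm temozolomide compliance but makes the means optional, and it sets no minimum temozolomide exposure for a patient to count in the escalation decision. Under-dosing in cycles 1-2 that is undetected or unclassified could let a level be cleared without the combination having been given as defined.

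The size cannot be computed from the documents. In the main illustration the chance of clearing a level with a true 35% DLT rate rises by 0.02 at 5% under-exposed and 0.04 at 10%, by 0.08 at 20% and 0.13 at one third. This rests on the assumed rates and on temozolomide adding to DLT risk. The likely effect is modest if adherence is good. The change is still worth making, because it is cheap and the missing data cannot be rebuilt later.

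**What to change.** In sections 4.0, 10.1 and 17.0, with a matching row in the section 6.0 calendar:

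1. Require diary review and a capsule count at the cycle 2 visit and at the pre-cycle 3 DLT evaluation.
2. Define a DLT-evaluable patient as one who has a DLT, or who received both infusions and at least a pre-specified share of the planned temozolomide doses in cycles 1-2. A share of 80% is only an example (0.80 × 28 = 22.4, so 23 of 28 daily doses); the sponsor should set it.
3. State that doses missed for toxicity leave the patient evaluable.
4. Replace other under-exposed patients for the MTD decision only, and keep them in the response analysis.

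**Cost.** A wording change and a count at two existing visits, plus perhaps one extra replaced patient in a cohort. In the main case a patient is replaced with probability r = f × (1 − 0.15), and a cohort of 6 needs on average 6r/(1 − r) replacements: 0.6 at f = 10% (r = 0.085) and 1.2 at f = 20% (r = 0.17).

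Counting every DLT but replacing under-exposed patients without one also makes the rule slightly cautious. The DLT rate among evaluable patients becomes q/(1 − r). At f = 10% this is 0.33/0.915 = 0.361, and P = 0.377 against 0.396 with full adherence. That is a smaller shift than the one removed (0.434), and it is in the safer direction.
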